database that delivers tailored, evidence-based sun safety emails/comments through the *Strava* interface based on predicted outside physical activity, forecast UV, and *personal skin cancer risk*. SS development will follow KB's standard iterative production. We will develop goals and behavioral objectives and outline of messages based on focus group results, theoretical models (see **3A.3**), GSS social media messages (see **Box 3**), and *sunZapp*'s advice algorithms (see **Box 2**). KB media developers will produce a database with the *Strava* API and algorithm predicting future outdoor physical activity (see **3C.4**) to power the SS interface and schedule sun safety messages (when and to whom). The SS database will determine time of day, date, location (from Wi-Fi, cellular network, or GPS), and forecast UV, and use *sunZapp* algorithm and outdoor physical activity algorithm to provide emails/activity comments over *Strava* platform advising precaution when UV Index is forecast to be ≥ 3 during predicted outdoor activity time (i.e., risk is moderate, high, or extreme based on Global UV Index standards⁹⁰). Messages will be sent at various times, based on outdoor activity algorithm (see **3C.4.2**); tentatively, we plan to deliver advice on the evening before outdoor activity bout to promote planning for sun safety (e.g., forecast UV Index for time outdoors; packing sunscreen and selecting hats, sunglasses, and protective clothing), just before predicted time of exercising, and during extended exercise (e.g., reapply sunscreen; use shade). We will ask focus groups about timing preferences (see **3C.3**). *Strava* users are accustomed to receiving emails/comments and most check them regularly (see **Box 1**). SS messages will be available through any device. Users will not need to interact with a separate app/interface. A specifications document with technical requirements, database plans, flow charts, and content outline will be developed.

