Eight months are allotted for the field trial. Participants will be enrolled on a rolling basis and participate in *SS* for 4 months in the intervention condition. After pretesting, participants will receive sun protection messages from *SS* through emails/comments based on algorithm results from their profile and activity data (see **3C.4**). All participants will complete posttest survey 4 months after randomization. They will receive links to both surveys via email and text and complete them using KB's QuestionPro software. Surveys will contain measures of self-efficacy, response-efficacy, sun protection practices, sunburn (defined as skin red and/or painful from exposure to the sun in the past four months),⁹⁶ and barriers to sun protection from the *sunZapp* and *GSS* trials (see **Boxes 1** and **2**), recall of *SS* messages (i.e., times they read the notifications; preferred type of message), and acceptability of receiving *SS* messages in future. We will assess physical activity behaviors at both pre- and posttest, using the validated International Physical Activity Questionnaire (IPAQ)^{97,98} long form and current activity data uploaded by participants to *Strava*. Intervention participants will be compensated \$65 total (\$30 pretest, \$35 posttest) and control group participants \$45 total (\$20 pretest, \$25 posttest).

3C.7. Data Management and Analysis

Focus groups will be recorded, transcribed, and analyzed using *Atlas-ti*® software by assigning codes that categorize views, themes, and opinions, rely on constant comparative analysis⁹⁹ and a phenomenological approach.^{100,101} In the pilot field trial, the primary outcome is change in sun protection pre to post, analyzed with a paired t-test; changes in perceived risk, response- and self-efficacy, and sunburn will be compared pre to post, similarly. Message recall (i.e. receipt of the messages), users' reactions, barriers, and willingness to use *SS*, will be summarized as proportions/means and compared on demographics (including if treatment differs as a function of biological sex), using chi-square tests, t-tests, and correlations at $p=0.05$ (2-tailed). We will likewise test if *SS* messages (message recall) reduced physical activity (IPAQ). Recruitment rates and duration, and follow-up rates, will be described to plan a future randomized trial on *SS*. Data will be de-identified and stored in KB's secure servers. [name] will oversee data analysis. SAS will be used for analyses.

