4. **Pilot Field Testers (n=226):** *Strava* users (n=176) will test the prototype *SS* interface while interacting with the *Strava* platform and community in the United States. They will be recruited through posting an invitation in *Strava* clubs. The invitation will link them to the study website where they will receive more information and be screened and consented. Participants will provide feedback on the design, appeal, and functionality of the *SS* message delivery and complete measures of self-efficacy, response-efficacy, sun protection practices, *sunburn (defined as skin red and/or painful from exposure to the sun in the past four months)*, and barriers to sun protection, recall of *SS* messages (i.e., how many times a day they read the notifications, how much they liked receiving them, preferred type of message), and acceptability and willingness to use *SS* interface through *Strava* in the future. Additionally, a small control group (n=50) will be included to determine if a no-treatment control condition is acceptable to *Strava* users and estimate follow-up rates for planning a randomized trial. The control group sample is not designed to test for statistical differences in comparison to the treatment group. *Randomization should assure that the control group is similar in age, gender, and activity level.* Inclusion criteria are 1) being 18 years of age or older, 2) writing and reading English, 3) being a regular user of *Strava* (at least 3 uploads per week), 4) living in the United States, and 5) consenting to participate. Exclusion criteria includes 1) having a cognitive or visual impairment that would interfere with participating, 2) having another family member participating in the research, or 3) being unwilling to give consent. They will also be excluded if they participated in a focus group or usability testing. Participants will be compensated \$65 (\$30 at baseline and \$35 at follow-up) for their time. Control group participants will be compensated \$45 (\$20 pretest, \$25 posttest) for completing the surveys.

Study Procedures, Materials, and Potential Risks.

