Focus groups will be recorded, transcribed, and analyzed using Atlas-ti[©] software by assigning codes that categorize views, themes, and opinions, rely on constant comparative analysis and a phenomenological approach. In the pilot field trial, primary outcome is change in sun protection pre to post, analyzed with a paired t-test; changes in perceived risk, response- and self-efficacy, and sunburn will be compared pre to post, similarly. Message recall (i.e. receipt of the messages), users' reactions, barriers, and willingness to use SS, will be summarized as proportions/means and compared on demographics, using chi-square tests, t-tests, and correlations at $p=0.05$ (2-tailed). Power analysis was estimated using treatment effect sizes from our sunZapp trials. For this small-scale pilot test, we powered on the quasi-experimental pretest-posttest comparison within the SS group, using a paired samples t-test. Assuming an effect size of 0.23 in sun protection pre to post and a correlation between the pre/post scores of 0.5, we will need 181 participants with complete pre-post data to detect an effect of this size with power of 0.80 in a 2-tailed $p=0.05$ test, which we factored up to 226 to account for 20% attrition. Recruitment rates and duration, and follow-up rates, will be described for planning a future randomized trial on SS effectiveness. We will test if sun safety messages (SS message recall) reduced physical activity (IPAQ), using correlations. The control group sample is not designed to test for statistical differences in comparison to the treatment group. Data will be de-identified and stored in KB's secure servers. [name] will oversee data management and analysis. SAS will be used for analyses.

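### The comparison of message recall across demographic groups takes no account of how many messages each person was sent, so delivery and reading cannot be told apart

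*Combined protocol and SAP*

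**What the plan says.** The SAP treats recall in one sentence with three other survey topics: "Message recall (i.e. receipt of the messages), users' reactions, barriers, and willingness to use SS, will be summarized as proportions/means and compared on demographics". The tests named are chi-square, t-tests and correlations at the two-sided 0.05 level. Section 3C.7 has the same sentence and adds biological sex.

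Three places describe what recall is, and they do not agree:
- The SAP and 3C.7 gloss it in parentheses as receipt.
- Section 3C.6 lists "times they read the notifications; preferred type of message".
- Protection of Human Subjects, item 4 (Pilot Field Testers), lists "how many times a day they read the notifications", together with liking and preferred message type.

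Section 3C.5.2 notes that Strava does not log whether a comment or email was read, so recall is self-reported at posttest.

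The number of messages is set person by person. Section 3C.5 has SS "advising precaution when UV Index is forecast to be ≥ 3 during predicted outdoor activity time", with a tentative schedule of the evening before, just before the bout, and during extended exercise. Section 3C.6 says messages come "through emails/comments based on algorithm results from their profile and activity data". According to 3C.5, the SS database is what will "schedule sun safety messages (when and to whom").

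Neither the SAP nor 3C.7 uses the number of messages sent as a denominator, a covariate or a tabulated quantity.

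**The concern.** Times read, whether in total or per day, depends on two things: how many messages the algorithm sent, and what share of them the person read. The planned comparison looks only at the result of both. If older users, women or one region turn out lower on recall, the analysis cannot say whether they ignored messages or were sent fewer. Someone whose bouts never qualify, and who is sent nothing, would count as low recall.

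The distinction matters for what a feasibility pilot can conclude. A delivery gap points to the prediction and trigger rules; a reading gap points to message content, timing or channel.

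**Working it through.** The plan gives no figure for this comparison, so there is none to reproduce. Its 181 completers belong to the primary paired test and play no part here.

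**1. Why the number sent varies.** For person i, messages sent are m = b × w × u × k.
- b, predicted bouts per week: 3C.6 expects 41% uploading on 5 or more days a week and 43% on 2 to 4.
- w, weeks: 4 months (3C.6), taken as 16.
- u, share of bouts with forecast UV Index of 3 or more: no figure given. In the Box 1 survey 53% exercised between 8am and 7pm but only 16% between 10am and 4pm. Recruitment is US-wide and enrolment is rolling, so place and season vary too.
- k, messages per qualifying bout: tentative in 3C.5, with extra messages in extended bouts.

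**2. What that does to recall.** Reads are r = m × s, where s is the share read. If s has the same mean in two groups and does not depend on m, the ratio of mean reads equals the ratio of mean messages sent. Example with u = 0.5, k = 2 and s = 0.5 (all assumed):
- 3 bouts a week: 3 × 16 × 0.5 × 2 = 48 sent, 24 read, or 24/112 = 0.21 a day.
- 5 bouts a week: 5 × 16 × 0.5 × 2 = 80 sent, 40 read, or 40/112 = 0.36 a day.

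Mean reads stand at 0.60 to 1, although both people read half of what they were sent. The per-day wording does not remove this.

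**3. Illustrative size.** The SS arm has 176 people; with 20% attrition, 176 × 0.8 = 140.8, or two groups of about 70. Assumed: 16 weeks; k = 2; uploads of 2, 3 and 5.5 a week in 16%, 43% and 41%; u uniform on 0 to 1; s from Beta(2,2) in both groups. One group is then sent 10%, 20% or 30% fewer messages.

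Check by hand, ignoring the small binomial variation:
- Mean uploads: 0.16×2 + 0.43×3 + 0.41×5.5 = 3.865. Mean reads: 32 × 3.865 × 0.5 × 0.5 = 30.9.
- Mean squared uploads: 0.16×4 + 0.43×9 + 0.41×30.25 = 16.91. Variance of reads: 1024 × 16.91 × (1/3) × 0.30 − 30.92² ≈ 776, so the SD is about 28.
- With 20% fewer sent: difference 0.2 × 30.9 = 6.2; standard error √(776 × (1 + 0.64)/70) = 4.26; z = 1.45. The chance of p < 0.05 is about P(Z > 1.96 − 1.45) ≈ 0.30. The same steps give about 0.11 for 10% and 0.63 for 30%.

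Simulated share of trials with p < 0.05 when both groups read the same share:

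| How recall is scored | Equal sent | 10% fewer | 20% fewer | 30% fewer |
|---|---|---|---|---|
| Count of reads, t-test | 4.3% | 10.5% | 28.3% | 61.6% |
| Reads per message sent, t-test | 4.4–5.2% throughout | | | |
| Four-level times-a-day item (cut-points assumed) | – | 5% | 13% | 28% |
| Any message read, yes/no, chi-square | – | 4% | 5% | 6% |

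The first two rows use 4,000 trials per scenario, the last two 2,000.

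**4. Sensitivity.** Narrowing u to 0.3–0.7 raises the count row to 14%, 46% and 86%. The 16% placed at 2 uploads a week fall below the eligibility minimum of 3; leaving them out changes the rates little. In a separate set-up with eligible frequencies only (3–4 or 5–7 bouts a week, 17 weeks, half of bouts qualifying), groups with 60% versus 40% high users had mean reads in the ratio 0.91. The count test was significant in 19% of trials and reads per message sent in 5.1%.

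**The case against.** The strongest reply is that the SAP never says it will compare raw counts of reads. It glosses recall as receipt, groups it with other items, and allows proportions and chi-square tests. A yes/no item would fit that wording and would be almost untouched. Receipt is also a legitimate quantity: a group that is sent fewer messages really is reached less, and a comparison of reach should show it. On that reading the 10%, 28% and 62% are power to detect a true difference in messages read. They are errors only if the question is whether groups read an equal share, which the SAP does not state.

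The remedy has limits too. Reads are remembered, not logged. Under 3C.5.2 one comment can produce an email, a dashboard alert and a phone notification, so reported reads can exceed messages sent. The near-5% rate for reads per message follows partly from simulating reads as a share of messages. Section 3C.5 describes scheduling, not a retained log for each person. Finally, the planning outputs named for the next trial are recruitment and follow-up rates, and no decision rule uses recall by demographics.

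All of this stands, and it limits the point. A reader might infer that the planned test has a false-positive rate of 28% or 62%, or that some group will be wrongly labelled unengaged. The documents support neither: they fix no scoring rule, state no null of equal share read, and report no demographic gap in sending. What survives is that the only concrete descriptions of recall are a number of reads and a daily frequency, and nothing planned separates delivery from reading.

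**Conclusion.** The point holds as an ambiguity in a secondary analysis. By design the number of messages differs between people, and recall is compared on demographics without regard to it. Any difference found could therefore come from the algorithm, the user or both.

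The size is unknown, because the documents do not show that any demographic group is sent fewer messages. The simulated rates are illustrations under an assumed gap, count scoring and a question about equal share read. With a coarse or yes/no item they shrink to between 4% and 28% over the same gaps. The primary paired pre-post analysis is unaffected. This is a cheap improvement, not a flaw that threatens the trial.

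**What to change.** In the SAP and 3C.7:
1. Adopt one definition and scoring rule for recall, and bring 3C.6, the Pilot Field Testers item and the SAP gloss into line with it.
2. State that the count of messages sent to each participant will be retained from the SS database.
3. Tabulate messages sent, including the number of participants sent none, by the same demographic groups.
4. Keep the planned recall comparison and label it as a measure of reach.
5. Add a comparison among participants sent at least one message that accounts for the number sent: for a count, a negative binomial model with log(messages sent) as an offset; for other scorings, messages sent as a covariate.

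The cost is SAP wording and one merge of the message counts with the posttest file, with nothing more asked of participants. The downsides are that participants sent none must be reported separately, and that the per-message figure is approximate because reads are self-reported and one message can generate several notifications. The SAP should say so.

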The feasibility of the *SS* intervention with adults *Strava* users ($n=226$) who consent to provide activity data will be tested in a pilot field test using a randomized pretest-posttest controlled design. Participants will be recruited through posts in *Strava* clubs. They will click on a link to learn more about the study and complete a screener (eligibility: 18 or older; reside in the United States; read/write in English; upload outdoor activity to *Strava* ≥ 3 times per week) and then be provided with a) consent form, b) authentication protocol to permit access to their *Strava* data, and c) pretest survey. Once our target sample is recruited ($n=226$ *Strava* users), we will disconnect the authentication. Based on our pilot data (**Box 1**), we anticipate that 41% will be high users (upload 5+ days per week) and 43%, medium users (upload 2-4 days per week). Participants will be randomized to either *SS* or untreated control group in a 3.5:1 ratio. Power analysis was estimated using treatment effect sizes from our *sunZapp* trials (**Box 2**). For this small-scale pilot test, we powered on the quasi-experimental pretest-posttest comparison within the *SS* group, using a paired samples t-test. Assuming an effect size of 0.23 in sun protection pre to post and a correlation between the pre/post scores of 0.5, , we will need 181 participants with complete pre-post data to detect an effect of this size with power of 0.80 in a 2-tailed $p=0.05$ test, which we factored up to 226 to account for 20% attrition. A small control group ($n=50$) will be included to see if a no-treatment control condition is acceptable to users and estimate follow-up rates for planning a randomized trial. It is not designed to test for statistical differences with the treatment group.

Randomization should assure that the control group is similar on age, gender, and activity level.

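### The figure of 226 is both the SS-group requirement and the two-arm total, so 181 SS completers cannot be reached, power is 0.77 rather than 0.80, and 181 does not follow from the stated inputs

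*Combined protocol and SAP*

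**What the plan says.** The same power calculation appears in protocol section 3C.6 (Pilot Field Trial) and in the Statistical Analysis Plan. It concerns one arm only: "we powered on the quasi-experimental pretest-posttest comparison within the SS group, using a paired samples t-test". The inputs are given as "Assuming an effect size of 0.23 in sun protection pre to post" and "a correlation between the pre/post scores of 0.5", tested two-sided at 0.05. The result is "we will need 181 participants with complete pre-post data to detect an effect of this size with power of 0.80", "which we factored up to 226 to account for 20% attrition".

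Section 3C.6 also makes 226 the whole recruitment target for the field trial. Those participants are randomised to SS or an "untreated control group in a 3.5:1 ratio", with a control group of 50. The human-subjects section (item 4, Pilot Field Testers) gives the same total of 226 and the split: "users (n=176) will test the prototype", with 50 controls. All three places say that the control group is not sized for a statistical comparison with the SS group.

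**The concern.** Two things look wrong.

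- **226 has two meanings.** It is derived as the number to enrol in the SS group so that 181 remain after attrition. It is then used as the number to enrol in both arms together. The 50 controls therefore come out of the SS requirement, although they contribute nothing to the powered test.
- **181 looks too large for its inputs.** A standardised change of 0.23 with correlation 0.5 should need about 150 pairs.

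This paragraph is the only sample-size justification for the declared primary outcome, the pre-to-post change in sun protection. Section 3C.1 says the field-trial analysis will test the hypothesis that SS improves sun protection. A null result would be read against a stated power of 0.80 that the design does not provide.

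**Working it through.** **Inputs** (section 3C.6, Statistical Analysis Plan, human-subjects item 4): effect size d = 0.23; pre/post correlation r = 0.5; two-sided alpha 0.05; power 0.80; attrition 20%; total 226; allocation 3.5:1; SS 176; control 50.

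**1. The plan's inflation step reproduces.** 181 / (1 − 0.20) = 226.25, which the plan gives as 226. So 226 is the enrolment needed in the SS group alone.

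**2. The allocation.** 226 × 3.5 / 4.5 = 175.8, so 176 in SS and 50 in control, as item 4 states.
- Completers at 20% attrition: 176 × 0.80 = 140.8, about 141.
- Shortfall against 181: 40 participants, 40 / 181 = 22%.
- With no attrition at all: 176 < 181.

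**3. The 181 does not reproduce.** For a paired t-test the relevant effect is dz = d / √(2(1 − r)). At r = 0.5 the divisor is √1 = 1, so dz = 0.23. The plan does not say whether 0.23 is scaled by the raw SD or by the SD of change, but at r = 0.5 the two coincide.
- Normal approximation: ((1.960 + 0.842) / 0.23)² = 148.4, so 149 pairs.
- Exact (noncentral t, n − 1 degrees of freedom): power is 0.799 at n = 150 and 0.802 at n = 151, so 151 pairs.

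Alternatives tried in search of 181:

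| Variant | Pairs needed |
|---|---|
| As stated | 151 |
| One-sided 0.05 | 119 |
| Power 0.85 | 172 |
| Power 0.90 | 201 |
| Two-sided alpha 0.025 | 183 |
| r = 0.40 | 180 |

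Only inputs that the plan does not state come close: r about 0.40 (equivalently dz about 0.209), or alpha 0.025. Note also that 151 × 1.2 = 181.2. Attrition may have been applied twice, but that is inference.

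**4. Power delivered for dz = 0.23, exact.**

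| SS completers | How it arises | Power | Effect detectable at 0.80 |
|---|---|---|---|
| 141 | 176 randomised, 20% attrition | 0.774 | 0.238 |
| 151 | 176 randomised, 14% attrition | 0.802 | 0.23 |
| 176 | 176 randomised, no attrition | 0.859 | 0.21 |
| 181 | the stated target | 0.868 | 0.209 |

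The attrition at which 0.80 is just kept is 1 − 151/176 = 14.2%. At 25% attrition (132 completers) power is 0.746, and at 30% (123 completers) it is 0.716.

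**5. If 181 rests on unprinted, less favourable inputs.** If 181 really is the number for 0.80 power, then dz is about 0.209, and 141 completers give power of about 0.69.

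**6. What 0.80 would require under the printed inputs.** 151 / 0.80 = 188.75, so 189 randomised to SS. The total is 189 + 50 = 239 with 50 controls, or 189 + 189/3.5 = 243 at 3.5:1.

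**The case against.** The arithmetic is not in dispute. The case on the other side concerns how much it matters.

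- **The loss is small.** Power falls by 2.6 points and the detectable effect moves from 0.23 to 0.238. Against the recomputed requirement of 151, the shortfall is 10 completers (about 7%), not 40. If SS attrition is 14% or lower, 0.80 is met. This stands, and it is why the size should be reported as 0.774 against 0.80 and not by the 22% alone. It does not rescue the paragraph, because 20% is the plan's own attrition assumption and 181 exceeds the whole SS group.
- **This is a feasibility pilot.** No decision rule depends on 0.80 rather than 0.77. That is true, but the plan names a primary outcome, a hypothesis test and a power, so the power should be correct.
- **151 may not be the right number either.** The effect size is attributed to the sunZapp trials and no formula is shown. This stands in part. The documents establish that 181 cannot be obtained from the printed inputs, not which input is at fault. The sponsor should say how 181 was obtained, and if it rests on other inputs the power is lower still, about 0.69.
- **Carry-over to the future randomised trial is not documented.** The plan says that recruitment and follow-up rates will inform that trial; it does not say that 181 or 0.80 will be reused. Carry-over is a risk worth avoiding, but the finding does not depend on it.

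**Conclusion.** The concern holds. The number 226 cannot be both the inflated SS requirement and the two-arm total. As planned, SS has 176 randomised and about 141 expected completers, so the stated 181 is out of reach at any attrition rate. The stated 181 is also not what the printed inputs give; they give 151. Because 181 is too high, the two errors partly cancel, and the power actually delivered for an effect of 0.23 is 0.774.

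This rests on the plan's own inputs (0.23, r = 0.5, two-sided 0.05, 20% attrition in SS) and a paired t-test on completers. No other part of the documents resolves either discrepancy.

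**What to change.** In section 3C.6 and the Statistical Analysis Plan, state the formula and inputs behind 181. If the printed inputs are the intended ones, replace the sentence with wording to this effect:

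> An effect of 0.23 with a pre/post correlation of 0.5 requires 151 complete pairs for 0.80 power (paired t-test, two-sided 0.05). Randomising 226 at 3.5:1 places 176 in SS; with 20% attrition about 141 complete both surveys, giving power 0.77 for 0.23 and 0.80 for an effect of 0.238.

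If other inputs were used, print them and recompute the power at 141 completers. Either way, make clear that 226 is the total for both arms. The cost is wording only, with a slightly less favourable stated power.

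If 0.80 at 20% attrition must be kept, there are two routes, each with a price:

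- **Add SS participants:** 189 SS + 50 control = 239, which is 13 more people.
- **Reallocate within 226:** 189 SS + 37 control. No extra participants are needed, but at 80% follow-up the 95% interval for the control follow-up rate widens from about ±11 points (1.96 × √(0.8 × 0.2 / 50)) to about ±13 (same formula with 37). Estimating that rate is one of the control group's stated purposes.

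Both routes also mean changing the allocation ratio and arm sizes in section 3C.6 and in human-subjects item 4. For a gain of under 3 points of power, restating the paragraph is the minimum and is enough.

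### The only stated check on whether SS lowers physical activity, a correlation of message recall with IPAQ, cannot show a reduction shared across the SS arm and, on posttest IPAQ, can hide some dose-related harm

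*Combined protocol and SAP*

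**What the plan says.** The Statistical Analysis Plan states: "We will test if sun safety messages (SS message recall) reduced physical activity (IPAQ), using correlations". Protocol section 3C.7 says the same with less detail ("messages (message recall) reduced physical activity (IPAQ"), pointing back to a list of chi-square tests, t-tests and correlations. IPAQ is not among the outcomes compared pre to post, and no analysis of Strava uploads is given for this question.

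The surrounding design matters:

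- **What triggers a message.** Section 3C.5 sends advice when the forecast UV Index is at least 3 during predicted outdoor activity. Section 3C.6 describes "emails/comments based on algorithm results from their profile and activity data". Section 3.C.5.2 attaches comments to uploaded activities.
- **What recall is.** Section 3C.6 has "times they read the notifications"; the Pilot Field Testers paragraph has "how many times a day they read the notifications"; the SAP equates recall with receipt ("Message recall (i.e. receipt of the messages"). Section 3.C.5.2 notes that actual reading is not recorded.
- **What is collected.** IPAQ is measured at pretest and posttest along with Strava uploads, without restriction to one arm, and "All participants will complete posttest survey 4 months after randomization".
- **What is left open.** The plan does not say whether posttest IPAQ or its change is correlated, on what scale, or whether controls enter.
- **Controls.** Section 3C.6, the Pilot Field Testers paragraph and the SAP each say that the 50 controls are not there for a statistical comparison.

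**The concern.** Section 3A.2 makes it a condition of the approach that sun safety advice should not put people off exercise. This correlation is the only stated analysis that bears on that condition, and it is worded as a test of whether messages reduced activity.

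There are two difficulties. First, a correlation within the treated arm compares heavier and lighter recallers with each other. It carries no information about a fall that both share. Second, more active people should be sent more messages by design. If recall follows messages sent, recall and posttest activity are positively linked before any effect of SS, which works against seeing harm. At stake is a null or positive coefficient being carried into the planning of the future randomized trial as reassurance it cannot give.

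**Working it through.** **Plan's own figure.** None is given for this correlation. The 181 completers in the SAP belong to the paired test of sun protection and play no part here.

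**Inputs from the documents.** SS arm 176, controls 50, attrition 20%. Applying 20% to each arm (my assumption): 176 × 0.8 = 140.8, about 141; 50 × 0.8 = 40. Two-sided 0.05.

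**Inputs assumed (not in the documents).** IPAQ pre/post correlation 0.6; correlation *a* of usual activity with messages sent, and *b* of messages sent with recall, each 0.3 to 0.7; mean IPAQ equal to 2 SD; messages follow usual activity, and harm does not reduce later message counts.

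**Step 1: significance threshold.** With n = 141, t(139) = 1.977, so critical |r| = 1.977/√(1.977² + 139) = 0.165.

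**Step 2: shared cut.** No simulation is needed for most of this. If posttest becomes (1 − c)·Y1 for everyone, corr(recall, (1 − c)·Y1) = corr(recall, Y1). On the log scale the cut adds a constant, so log change is unaffected too. For raw change, with r0 the no-effect posttest correlation:

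r = −c·r0 / √[(1 − c)² + 1 − 2(1 − c)(0.6)]

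With r0 = 0.19, cuts of 10%, 20% and 30% give r = −0.02, −0.05 and −0.07, significantly negative in about 4%, 8% and 14% of simulated trials. The sensitivity that remains comes only from the confounding: with r0 = 0 it disappears.

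**Step 3: upward bias on posttest IPAQ, no effect of SS.** r0 = a·b·√0.6.

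| a, b | r0 |
|---|---|
| 0.3, 0.3 | 0.09 × 0.775 = 0.07 |
| 0.5, 0.5 | 0.25 × 0.775 = 0.19 |
| 0.7, 0.7 | 0.49 × 0.775 = 0.38 |

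At 0.5/0.5, simulation gave a significant positive r in 62% of trials and a significant negative r in about 0%. If either link is zero, the bias is zero. A separate count-based simulation (lognormal bouts per week, Poisson messages, other inputs also assumed) gave no-effect r of +0.24 to +0.50 with exact recall, +0.12 to +0.25 with noisy recall, and 0.00 when recall is unrelated to activity.

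**Step 4: dose-related harm.** Let activity fall by h SD per SD of recall.

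- Posttest: r = (r0 − h)/√(1 + h² − 2h·r0). With r0 = 0.19, h = 0.2 gives r = −0.01, detected in 4% of trials (66% without confounding); h = 0.3 gives −0.11, 25% (94%); h = 0.5 gives −0.30, 96%.
- Change: r = −h/√(0.8 + h²). h = 0.2 gives −0.22, detected in about 75%; h = 0.3 gives −0.32, 97%.

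These figures hold only with no feedback from harm to message counts. In the count-based model, posttest IPAQ with exact recall and average harm near 20% was significantly negative in 0 to 37% of trials when reduced activity also lowers later messages. Without that feedback the upper end was between about 66% and 81%, depending on set-up.

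**Step 5: change scores with no effect.** If activity drifts over the trial, the count-based model gives r from 0.00 to +0.29 when messages follow in-trial activity, and from −0.29 to −0.04 when they follow activity around pretest. The bias can go either way.

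**Step 6: controls pooled at recall zero.** A shared 20% cut then shows, but was significantly negative in only 0 to 48% of trials across readings.

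**Step 7: what an arm comparison could show.** SE in SD units = √(1/141 + 1/40) = 0.179. Detectable difference at 80% power = (1.96 + 0.842) × 0.179 × √(1 − ρ²), with ρ the pre/post correlation: 0.50, 0.43 and 0.40 SD for ρ = 0, 0.5 and 0.6. At ρ = 0.5 the 95% CI half-width is 1.96 × 0.179 × 0.866 = 0.30 SD. For a uniform 20% cut on the log scale (ln 0.8 = −0.223), assumed IPAQ noise of 0.35 log SD gives a 95% CI factor of 1.16 to 1.23 and power 0.54 to 0.84; noise of 0.7 gives 1.31 to 1.36 and power 0.29 to 0.38.

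**The case against.** The strongest reply is that change is at least as natural a reading as posttest, since IPAQ is taken twice and the question is whether activity was reduced. On change scores, dose-related harm is often detected and the upward bias may vanish or reverse. That stands, and it limits the masking claim mainly to posttest IPAQ. It does not restore sensitivity to a shared cut.

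A second reply is that harm from messages should vary with exposure, so an identical cut in people who read almost nothing is a stress case. This is fair as to likelihood. But an effect need not be identical in everyone to be missed: whatever part of a reduction is common to the arm is invisible, and the plan gives no reason to assume that part is nil.

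Third, the control group is explicitly not meant for testing, and an arm comparison will also be imprecise. True; that is why only an estimate with its interval is proposed.

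Two stronger inferences should be resisted. A reader might conclude that the correlation would always miss harm. It would not: large dose-related harm usually shows, and if recall is unrelated to activity the upward bias disappears. A reader might also take the disconnection of authentication in section 3C.6 to mean that Strava data stop once recruitment closes. Section 3C.5.1 ends data access at the end of the study, and section 3C.6 plans activity-based messages for four months, so the disconnection more plausibly closes new sign-ups.

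**Conclusion.** The point holds in limited form. Blindness to a proportional cut shared by the SS arm is exact for posttest IPAQ and for log change. On raw change the signal is weak (about 4 to 14% detected for cuts of 10 to 30%, under the stated assumptions). The upward bias on posttest IPAQ follows in direction from activity-triggered messages, but only to the extent that recall tracks messages sent. Its size (about +0.07 to +0.38 in one model, +0.12 to +0.50 in the other) rests on assumed inputs. Some dose-related harm can be hidden on posttest IPAQ; no single percentage is defensible, because it depends on recall accuracy and on whether reduced activity lowers later message counts.

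The practical conclusion is that a null or positive r does not show that SS leaves activity unchanged. This is a secondary analysis in a feasibility pilot. It does not touch the primary outcome or the sample size, and the documents do not support reading it as a flaw in either. It should be corrected before analysis.

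**What to change.** 1. Add an exploratory model of posttest IPAQ (log or rank scale) on arm and pretest IPAQ, reporting the SS-versus-control estimate with a 95% CI. Label it estimation, and state that an interval including no difference is not evidence of no reduction.
2. Show pre-post IPAQ change in each arm beside it. The SS change alone cannot be separated from season, since "Participants will be enrolled on a rolling basis".
3. Keep the recall correlation as a secondary description within SS. Fix one definition of recall, exclude controls, and state the IPAQ score and scale. Use IPAQ change or adjust for pretest IPAQ, and note that confounding remains: in the count-based model, adjusting the posttest correlation still left no-effect r at +0.15 to +0.45 with exact recall and +0.07 to +0.22 with noisy recall.
4. Show the same arm comparison on the Strava uploads already planned, where they are available in both arms.

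The cost is SAP wording and one additional model, repeated on uploads; no new IPAQ data are needed. The downside is a wide interval: a detectable difference of roughly 0.40 to 0.50 SD, and power of about 0.3 to 0.8 for a uniform 20% cut, depending on IPAQ noise that the documents do not give. For moderate dose-related harm the correlation can be the more sensitive analysis, which is why it is kept.
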